6.3 Follow-up of adverse events

All AEs will be followed until they have abated, or until a stable situation has been reached. Depending on the event, follow up may require additional tests or medical procedures as indicated, and/or referral to the general physician or a medical specialist.

SAEs need to be reported till end of study within the Netherlands, as defined in the protocol.

6.4 Incidental medical findings

Incidental medical findings for which medical follow-up is required will be reported to the patient self and his/her general practitioner. Patients who do not wish to know about incidental findings are not allowed to participate in this study. This is also mentioned in the informed consent form of this study.

7. STATISTICAL ANALYSIS

7.1 Primary study parameters

CMR qualitative and quantitative analyses will be performed on a dedicated work-station with counseling of investigators experienced in the post-processing of CMR techniques.

The included data will be presented as mean \pm standard deviation. Ratios will be given for statistical assessment of non-continuous variables. Correlation analyses will be used to analyze differences between continuous parameters. Confidence intervals (95%) will be used and a $p < 0.05$ will be considered statistically significant. Fisher exact test will be performed to verify significance, risk ratio (RR) and 95% confidence intervals. SPSS 26.0 (SPSS Inc, Chicago, IL) for Windows is used to assess statistical analyses.

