4. STUDY POPULATION

4.1 Population (base)

The research population consists of MVI patients scheduled for elective surgical mitral valve repair conform the current guideline criteria.

These patients will be recruited from the surgery-waiting list / database of the AUMC after they have been accepted for surgery by a multidisciplinary heart team.

Data from a control group of non-MVI/AF age-sex matched controls (N=10) will be retrieved from an existing database. These controls have undergone the same MRI scan protocol for a different medical indication.

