4.4 Sample size calculation

This study is designed as a pilot study, since we are the first to assess the effect of LA fibrosis and its characteristics prior to and after mitral valve repair surgery.

Therefore we aim to include;

- 20 patients with MVI which are admitted to mitral valve repair surgery

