5. METHODS

5.1 Study parameters/endpoints

5.1.1 Main study parameter/endpoint

The main study parameters are:

1. Severity of MVI prior to and after surgery (defined as regurgitation volume in ml)
2. Left atrial remodelling prior to and after surgery
 - Left atrial volume
 - Calculated left atrial sphericity
 - Estimated wall tension (wall thickness, radius, pulmonary wedge pressure)
 - Mitral regurgitation flow measurement (quantitative)
3. Presence and distribution patterns of LA fibrosis
 - Quantification of fibrosis surface (severity)
 - Geometric distribution of fibrosis (localization)
4. Blood flow patterns in the LA (4D Flow)
 - Flow velocity (mean and peak)
 - Static fraction
 - Kinetic energy

Secondary study parameters/endpoints -Fibrosis associated biomarkers derived from blood samples (NT-proBNP, TNF- β , Angiotensin II, cytokines)

-Heart failure symptoms monitoring derived from questionnaire preoperative and at postoperative follow-up

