7.3 Other study parameters

Continuous data will be presented as mean with standard deviation or median with range. Categorical data are presented as proportions. Tables will summarize patient characteristics, clinically relevant parameters and routine MRI parameters (enddiastolic and endsystolic volumes, stroke volume, ejection fraction).

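### Section 7.1 offers only mean ± SD and an unspecified correlation for main parameters, some of which are likely to be skewed near zero after repair

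*Combined protocol and SAP*

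**What the plan says.** Section 7.1 (Primary study parameters) gives one summary for the main data: "The included data will be presented as mean" ± standard deviation. For continuous measures it adds "Correlation analyses will be used to analyze differences between continuous parameters", then "Confidence intervals (95%) will be used" and a 5% significance threshold. It has a separate route for non-continuous variables (ratios, Fisher exact test, risk ratio). It does not mention a median, a transformation, a rank method or a check of distribution. It does not say which correlation is meant, how the intervals are built, or which paired comparison will be made.

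Section 7.3 (Other study parameters) is more flexible: "Continuous data will be presented as mean with standard deviation or median with range". That sentence does not extend to the main parameters.

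Section 5.1.1 lists the main parameters, beginning with "Severity of MVI prior to and after surgery (defined as regurgitation volume in ml"). Fibrosis surface, static fraction and kinetic energy are also on the list. Section 4.4 sets the size at "20 patients with MVI which are admitted to mitral valve repair surgery" and describes the study as a pilot. It gives no SD, effect size, power or precision target.

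**The concern.** Regurgitation volume, fibrosis surface, static fraction and kinetic energy cannot be negative. Section 4.2 admits patients with severe insufficiency, and the valve is then repaired. After surgery, regurgitation volume should therefore sit at or near zero in most patients, with a few residual leaks. For data of that shape, mean ± SD describes the group poorly, and a standard interval for the mean tends to cover less than its nominal 95% in a small sample.

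Section 5.2 also plans to relate atrial remodelling to quantitative regurgitation. If that is done with an untransformed correlation on post-repair data, one or two patients with a leak may decide the result. At stake are the description of the post-repair state and the credibility of the reported associations. A further risk is that the choice between mean and median, or between raw and rank correlation, is made after the data are seen.

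**Working it through.** **No figure to reproduce.** The plan states no power, SD or interval width, so the question was tested by simulation.

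**Inputs from the documents.** n=20 (section 4.4); 95% intervals and p<0.05 (section 7.1, taken as two-sided). Section 5.2 excludes poor images and section 5.4 deletes the data of withdrawn patients, so 20 is an upper limit.

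**Assumptions, not in the documents.** Log-normal or gamma data with CV 0.3 to 1.5, or 30 to 70% exact zeros. For log-normal data the log-scale SD is σ = √ln(1+CV²), for example 0.83 at CV 1. There were 40,000 runs per scenario, with simulation error of about 0.1 point.

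**1. Mean at a single time point.** Interval: mean ± t × SD/√n, with t = 2.093 on 19 df, so the half-width is 2.093/√20 = 0.468 SD.

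| Assumed data | Coverage of the nominal 95% interval |
|---|---|
| Normal | 94.9% |
| Log-normal, CV 0.3 / 0.5 / 0.75 | 94.2 / 93.3 / 91.1% |
| Log-normal, CV 1.0 / 1.5 | 89.3 / 85.4% |
| Gamma, CV 0.5 / 1.0 / 1.5 | 94.3 / 91.7 / 88.9% |
| 30 / 50 / 70% zeros, rest log-normal with CV 1 | 89.6 / 88.7 / 85.3% |

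**2. An illustrative post-repair regurgitation volume.** Assume 60% exact zeros and the rest log-normal with mean 10 ml and CV 1.
- Mean = 0.4 × 10 = 4 ml.
- Mean square = 0.4 × (10² + 10²) = 80, so variance = 80 − 16 = 64 and SD = 8 ml.
- The prescribed summary would read 4 ± 8 ml, and mean minus SD is −4 ml, which is impossible. The interval for this mean covers about 87%.

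**3. Before/after change.** Interval: mean difference ± t × SD of differences/√n.
- Regurgitation volume as in step 2, with an assumed 60 ± 20 ml before repair: coverage about 95%.
- Log-normal values, 35% fall, correlation 0.7, CV 0.6 / 1.0 / 1.5: coverage 94 / 92 / 91%.
- After/before ratio 1.0, 1.3 or 1.5, log-scale correlation 0.5 or 0.8: 94.0–95.3% at CV 0.5, 91.5–96.1% at CV 1.0, 89.7–96.8% at CV 1.5. The lowest value comes from the strongest skew, largest change and higher correlation together. With no true change the interval does not under-cover. At n=16 the overall range is 89.4–97.0%.

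**4. Correlation, if Pearson is used.** Interval on the Fisher scale: atanh(r) ± 1.96/√17 = atanh(r) ± 0.475. With an underlying log-scale correlation of 0.5 to 0.6, coverage is 95% for normal data, 91–92% at CV 0.5, 85–87% at CV 1.0 and 80–83% at CV 1.5. With zero correlation it stays at 94–95%.

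**5. Leverage of one patient: a limiting case.** Suppose 19 of 20 post-repair volumes are zero and one patient leaks. If that patient lies d standard deviations from the mean on the other variable, then r = d / √(19 × (1 − 1/20)) = d/4.249, whatever the size of the leak. With d = 2, r = 0.471, above the 5% critical value of 0.444 for n=20. Spearman in the same case is limited by the ranks: the largest possible d is (20 − 10.5)/√35 = 1.606, giving 1.606/4.249 = 0.378.

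**The case against.** The case against is strong on several counts.

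- **The plan does not prescribe the weak methods.** Section 7.1 names neither Pearson, nor a paired t-test, nor an interval method. Spearman or bootstrap intervals would already comply. Only a descriptive format is fixed. This stands: the fault is an open choice and a missing median.
- **A bound at zero does no harm by itself.** The mean must lie close to zero relative to the SD, and no SD is given. This also stands. No argument is available for left atrial volume, sphericity, wall tension or velocity, so the point cannot be extended to every main parameter.
- **The primary objective concerns the period before and after surgery.** Differencing removes much of the skew, and for regurgitation volume the large fall swamps what remains. Step 3 bears this out.
- **This is a pilot that claims no power.** No stated figure is contradicted.

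A reader might infer that the 95% intervals are simply wrong and that real changes will be missed. The documents do not support that. Coverage depends on a degree of skew they do not report. Power depends on a paired test they do not name, and at CV 0.5 with a ratio of 1.3 the paired t-test and Wilcoxon test both have 59% power.

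What survives is narrower. The main parameters lack the median that section 7.3 gives the lesser ones, and the design makes skew in post-repair regurgitation volume plausible.

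**Conclusion.** The point holds as a modest improvement, not as an error that undermines the study. If skew is marked, a single-time-point mean at n=20 has an interval that covers about 85 to 90% instead of 95%, and an untransformed correlation can turn on one or two patients. For the before/after change the shortfall is usually no more than about 4 points. At CV 0.5 it is about 2 points for a single mean and 3 to 4 points for a Pearson interval. All of this rests on assumed distributions, and the pilot's own data will show which case applies.

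A related gap in the same section matters at least as much. A correlation measures association and does not estimate a before/after difference, so changing the summary measure alone would leave the primary comparison unspecified.

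**What to change.** In section 7.1:

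- Summarise regurgitation volume, fibrosis surface, static fraction and kinetic energy by median and interquartile range.
- Report each before/after change as a paired estimate with a 95% CI, in place of a correlation. Where the data are skewed or contain zeros, use the Hodges-Lehmann estimate with the Wilcoxon signed-rank test.
- For associations involving these four parameters, name Spearman correlation with a bootstrap CI.

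This is SAP wording only, with no extra patients, scans or visits. It should be settled before the data are analysed. The cost is a small loss of efficiency if the data are in fact normal: at n=20 and a true correlation of 0.6, power is about 77% with Spearman against 83% with Pearson. At CV 0.5 the two are equal at 77%, and at CV 1.0 Spearman has 77% against 67%.

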post-processing techniques prior to and after mitral valve repair surgery to gain insight on the clinical role and predictive value of atrial fibrosis in this patient population.

In addition, we aim to assess the effects of (reduced) volume overload on atrial wall texture, geometry and function.

It is hypothesized that the atrial fibrosis surface area paradoxically will increase after mitral valve surgery because of global shrinkage of the LA caused by the reversed remodeling process.[1] As a consequence, more frequently atrial fibrosis related events including (paroxysmal) AF, may be observed in these patients.

With this insight, CMR can become clinical valuable for the indication and timing of surgical intervention in these patients. Surgical therapy might be renounced for example when a substantial increase of fibrosis surface is expected post-surgically causing a higher risk for AF, HF, PH and a reduced quality of life. On the contrary, surgical therapy might be considered in an earlier stage of disease when the amount of fibrosis is still limited regarding its expected post-surgical development.

[figure not shown]

Figure 1. Pathway to structural LA remodeling caused by a pathological trigger.

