2. OBJECTIVES

Primary Objective:

To assess

- the effects of (reduced) volume overload on the left atrial wall texture (presence, amount and location of atrial fibrosis) and associated geometry and function in patients with MVI, prior to and after elective mitral valve repair surgery.

Secondary Objectives:

To assess;

- the value of LA fibrosis in stratification and timing of mitral valve repair surgery.
- the impact of atrial fibrosis on myocyte contractile function (atrial strain, quantified by CMR).
- whether left ventricular (LV) volume overload results in increased extra cellular volume (ECV) and whether this is reversible after mitral valve repair surgery.
- the impact of LA remodeling on right atrial (RA) function and tissue characteristics.
- the predictive value of LA fibrosis for outcomes of AF and atrial function during post-surgical follow up

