3. STUDY DESIGN

This study is designed as a single center pilot study. The aim of this study is to assess the role of left atrial fibrosis and its characteristics prior to and after mitral valve repair surgery in MVI patients.

Study subjects that will be included are MVI patients who meet the criteria for mitral valve repair surgery and are on the waiting list for elective surgery. Exclusion criteria are: AF, history of cardiac surgery, comorbidities, MRI contra-indications. The study subjects are recruited from the Amsterdam UMC surgical waiting list.

The study subjects will visit the AmsterdamUMC hospital (Location VUmc) two weeks prior to mitral valve repair surgery for a CMR scan. This visit will start with checking in- and exclusion criteria using questionnaires regarding medical history and MRI safety. The total duration of the visit, including the CMR scan, will be approximately two hours.

[figure not shown]
Two weeks later the subjects will undergo mitral valve repair surgery (Location AMC). During anesthesia, a Swan-Ganz catheter will be used for hemodynamic monitoring. This Swan-Ganz catheter is part of the standard care for mitral valve repair surgery.

At three months follow-up, subjects will visit the AmsterdamUMC hospital (Location VUmc) for a second CMR scan to assess reversed atrial remodeling and amount of fibrosis.

Image data from age and gender matched controls will be retrieved from an existing database. The patients in this database have undergone the same MRI scan protocol (for a different medical indication) as scheduled for our study population. Only data from patients without MVI and AF will be used from the database for reference. Absence of MVI and AF will be confirmed by checking ECGs and echocardiography of the control patients.

See *figure 2* for a schematic representation of the study design.

Figure 2. Schematic representation of the study design: Left atrial remodeling in MVI

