In the occurrence of a clinical relevant incidental finding patients will be informed by their treating physician. During the informed consent patients will be notified of this obligation. Patients who refuse to be informed about clinical relevant incidental MRI findings, will be excluded from this study.

MRI processing

Quantification of LA fibrosis will be performed using commercially available ADAS 3D LA image post-processing software (Galgo Medical, Barcelona, Spain) and open-source CEMRG image post-processing software (King's College London, United Kingdom). The 3D LGE images will undergo stringent quality control (i.e. artefacts, proper myocardial nulling) by two experienced readers prior to post-processing and images will be excluded from analysis if quality is deemed insufficient.

[figure not shown]

Figure 3. Left atrial 3D reconstruction from MRI.

Left Atrial remodeling

LA remodeling will be assessed by quantifying atrial sphericity and calculation of the wall tension calculation using Laplace's law ($T = p \times r / 2T$). This calculation includes pulmonary wedge pressure which is determined using peri-operative Swan-Ganz based pressure measurements during anesthesia, and radius based on atrial volume and wall thickness. Also the relation to quantitative MVI will be determined using 4D-flow MRI processing.

Presence and distribution of LA fibrosis

Quantification of fibrosis surface and the distribution of fibrosis will be assessed using LA 3D reconstructions based on 3D MRA data. Output of this data will be as shown below in Figure 4. The left atrial wall is segmented for accurate geometric localization of fibrosis (*Figure 4A*) and the severity of fibrosis will be shown as quantified surface area (*Figure 4B*).

[figure not shown]

Figure 4. Left atrial segmentation (A) for accurate assessment of geometric distribution of fibrosis and severity of fibrosis shown as quantified surface (B).

4D Flow

4D-flow data will be corrected for Maxwell terms in the image reconstruction at the scanner, and velocity aliasing during post-processing. 4D flow data will be co-registered with the cine images to guide left atrial anatomic orientation. Mean and peak flow velocity data will be derived using dedicated research software (MASS version 2017-Exp, Leiden University Medical Center, Leiden, the Netherlands). Furthermore, the volume fraction in the left atrium with a flow velocity below 10cm/s during the entire cardiac cycle will be determined.

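### Section 7.1 assigns correlation to analysing differences, so the before/after change that is the primary objective has no valid test

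*Combined protocol and SAP*

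**What the plan says.** The question is a paired one throughout. Section 1 states the hypothesis: "It is hypothesized that the atrial fibrosis surface area paradoxically will increase after mitral valve surgery". The primary objective in Section 2 covers atrial fibrosis and "associated geometry and function in patients with MVI, prior to and after elective mitral valve repair surgery". Section 3 brings the same patients back at three months "for a second CMR scan to assess reversed atrial remodeling and amount of fibrosis". Section 5.1.1 lists regurgitation volume before and after surgery as the first main parameter, and "Left atrial remodelling prior to and after surgery" as the second.

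For the analysis of these parameters, Section 7.1 offers:

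- mean and standard deviation;
- ratios for non-continuous variables;
- for continuous ones, "Correlation analyses will be used to analyze differences between continuous parameters";
- 95% confidence intervals, without saying of what;
- a 0.05 significance level;
- Fisher's exact test with a risk ratio.

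Section 7.2 says only which department analyses the blood samples. Section 7.3 is descriptive. No paired t-test, signed-rank test, mixed model, McNemar test or interval for a mean change is named anywhere in the document.

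**The concern.** Correlation measures whether patients who are high at one scan tend to be high at the other. It says nothing about whether the group as a whole moved. If Section 7.1 is followed as worded, two errors are possible. A parameter that did not change, but orders patients similarly at both scans, would be reported as significantly different. A real change with a weak pre/post correlation would be missed.

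If the sentence is read more generously, as being about associations between different parameters, its p-values are valid. The test of the main hypothesis is then unspecified and will be chosen once the data are in hand. On either reading the central comparison is not covered.

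Reporting a mean and SD at each time point does not repair this. The confidence interval of a within-patient change needs the individual differences, or equivalently the pre/post correlation, and neither can be recovered from the two summaries.

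**Working it through.** **Inputs from the plan.** 20 MVI patients (Section 4.4), each scanned before surgery and at three months (Section 3); significance at p<0.05 (Section 7.1). The sample size has no effect size, SD or power behind it, so there is no figure of the plan's own to reproduce.

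**Assumptions.** Two-sided testing, normal data, equal SDs at the two scans and 20 complete pairs. The plan gives no pre/post correlation ρ, so 0, 0.3, 0.5 and 0.7 are used.

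**1. Correlation ignores a shift.** For any constant c, corr(pre, post + c) = corr(pre, post). In one simulated set of 20 pairs, adding 0, 5, 10 or 50 units to every post value left r = 0.562 and p = 0.0099 unchanged. The paired t statistic went from -0.12 (p = 0.91) to 4.5, 9.1 and 46.0.

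**2. How often the correlation test is significant.** The test statistic is t = r√(18/(1−r²)) on 18 degrees of freedom. Its rejection rate depends on ρ and not on the shift. It was simulated with 40,000 trials for each combination of ρ and a shift of 0, 0.5, 0.8 or 1.0 SD. At ρ = 0.5 the rates across the four shifts were 64.8%, 64.4%, 64.0% and 63.9%, with no trend beyond simulation error. The table pools over shifts.

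**3. Paired t-test for a 0.8-SD change.** The SD of the change is SD·√(2(1−ρ)). The noncentrality is therefore 0.8·√20/√(2(1−ρ)), with 19 degrees of freedom. For ρ = 0.5 this is 0.8 × 4.472/1 = 3.58.

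| ρ | Correlation p<0.05 (any shift, including none) | Paired t, no change | Paired t, 0.8-SD change |
|---|---|---|---|
| 0 | 5.1% | 5% | 67.0% |
| 0.3 | 25.5% | 5% | 81.8% |
| 0.5 | 64.3% | 5% | 92.4% |
| 0.7 | 95.6% | 5% | 99.2% |

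At ρ = 0 a real 0.8-SD change would be flagged in about 5% of trials instead of 67%. At ρ = 0.7 an absent change would be flagged in about 96% instead of 5%.

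**4. Precision from separate summaries or from paired differences.** These are 95% half-widths for the mean change, in units of the SD at one scan.

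- Two separate means and SDs: t(38) × √(2/20) = 2.024 × 0.316 = 0.64.
- Paired differences: t(19) × √(2(1−ρ)/20) = 2.093 × 0.316, 0.265, 0.224 and 0.173, giving 0.66, 0.55, 0.47 and 0.36 at the four values of ρ.

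**5. What the paired analysis can deliver.** With 20 pairs, a paired t-test has 80% power for a mean change of 0.66 SD of the change, and the 95% half-width is 0.47 SD of the change. Section 5.2 excludes poor-quality images and gives no rate. If only 14 pairs remained (assumed), these figures become 0.81 and 0.58.

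**6. Fisher's test does not fill the gap.** It does not apply to continuous parameters. For a yes/no parameter it ignores the pairing. With 8/20 before and 14/20 after, 6 patients gaining and none losing, Fisher gives p = 0.11 and exact McNemar p = 0.031.

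**The case against.** The best defence is that the sentence is loosely worded and refers to relations between different parameters. The plan does have such questions: Section 5.2 relates atrial remodelling to quantitative regurgitation, and Section 2 asks how fibrosis affects atrial strain. On that reading correlation is legitimate, the fault is an omission and not a wrong test, and the rejection rates in the table do not apply. That is fair as to the rates. It leaves the gap in place, because no test of change is then named.

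A second argument is that this is a single-center pilot and could be purely descriptive, or that the promised 95% intervals may be meant for the mean change. However, Section 7.1 sets a significance threshold, Section 1 states a directional hypothesis, and the interval sentence names no quantity. A descriptive pilot would still need the within-patient change and its interval.

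Three limits stand:

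- The precision gain depends on an assumed correlation. At ρ = 0 the paired interval is slightly wider (0.66 against 0.64 SD).
- Twenty complete pairs is a best case, given the image exclusions in Section 5.2 and the deletion of withdrawn patients' data in Section 5.4.
- No yes/no before/after comparison is explicitly planned, and Fisher's test is not prone to false positives there. With 50% at both times it rejects in 2.0%, 1.0% and 0.2% of trials at phi 0, 0.2 and 0.5. For a rise from 50% to 80% its power is 41%, 39% and 36%, against 37%, 43% and 58% for McNemar. That point is secondary and adds nothing to the severity.

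**Conclusion.** The concern holds, and this must be fixed before analysis. The rule as written, applied to the plan's main question, answers a different one. Read generously, it leaves that question without a test. The insensitivity of correlation to a uniform shift is a mathematical fact and needs no assumption about the data.

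The size depends on the reading. Taken literally, the chance of declaring a difference is set entirely by the pre/post correlation (about 5% to 96% over the range 0 to 0.7), whether or not anything changed. This shows what the literal rule does and is not a forecast of the trial's error rate. Read as associations only, the cost is an analysis left open until the data are seen, and summaries that cannot give the interval of the change. At an assumed correlation of 0.5 that interval would have a half-width of 0.47 SD from paired differences, against 0.64 SD from the separate means. All figures assume normal data, equal SDs, two-sided testing and 20 complete pairs.

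**What to change.** Replace the correlation sentence in Section 7.1 with wording such as:

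> Continuous main parameters measured before and after surgery will be analysed as within-patient change (post minus pre) with a 95% CI, by paired t-test, or by Wilcoxon signed-rank test for parameters listed in advance as likely to be skewed. Correlation will be used only for associations, for example change in fibrosis with change in regurgitant volume.

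Listing the signed-rank parameters beforehand keeps the choice of test from depending on the results.

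Apply this to wall tension only if a post-surgery pressure exists. Section 5.2 bases it on "pulmonary wedge pressure which is determined using peri-operative Swan-Ganz based pressure measurements during anesthesia", and no pressure at three months is described.

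Add one conditional sentence: if any yes/no parameter is compared before versus after surgery, use the exact McNemar test with a paired estimate and CI. Keep Fisher's test and the risk ratio for independent groups. Examples are baseline fibrosis against later AF, which serves the secondary objective on "the predictive value of LA fibrosis for outcomes of AF and atrial function during post-surgical follow up", or patients against controls if these are not individually matched.

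The cost is one replaced sentence and one added. Parameters measured at both scans need no new data, and SPSS, which the plan already names, runs these tests. Only a before/after comparison of wall tension would need a measurement that the plan does not describe.

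### Section 7.1 gives Fisher's exact test with a risk ratio as the only method for non-continuous outcomes, assigns it to no contrast, and names no paired method for the before/after fibrosis comparison

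*Combined protocol and SAP*

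**What the plan says.** The primary objective (section 2) covers "presence, amount and location of atrial fibrosis) and associated geometry and function in patients with MVI, prior to and after elective mitral valve repair" surgery. Section 5.1.1 lists "Presence and distribution patterns of LA fibrosis" among the main study parameters. Section 4.4 sets the size at "20 patients with MVI which are admitted to mitral valve repair surgery". Section 3 has each patient scanned two weeks before the operation and recalled at three months "for a second CMR scan to assess reversed atrial remodeling and amount of fibrosis". Presence and location are therefore observed twice in the same people.

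On analysis, section 7.1 says "Ratios will be given for statistical assessment of non-continuous variables", then "Fisher exact test will be performed to verify significance, risk ratio (RR) and 95% confidence intervals", with p below 0.05 as the criterion for significance. Its correlation analyses are reserved for continuous parameters. Sections 7.2 and 7.3 name no test. No McNemar test or other paired categorical method appears anywhere, and section 7.1 does not say which contrast the Fisher sentence is for.

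**The concern.** Fisher's exact test and the usual risk-ratio (RR) interval are methods for two independent groups. If an analyst follows section 7.1 for the before/after question, 20 pairs become two groups of 20, and the information on which patients gained or lost fibrosis is discarded. Two scans of one atrium three months apart would normally be positively correlated. The unpaired interval is then too wide, and a real change in presence may be reported as not significant. In a study of 20 patients that loss counts.

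Location adds a second form of dependence, because each patient contributes several atrial segments. The plan does not say how these are to be handled.

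**Working it through.** The plan states no power, effect size or event rate, so there is no figure of its own to reproduce.

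**Inputs.** From the documents: 20 patients (section 4.4), two scans each (section 3), significance at 0.05 (section 7.1). Assumed, because the documents are silent: a two-sided test, 20 complete pairs, and all prevalences and correlations.

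**Step 1: what ignoring the pairing does to one result.** Suppose fibrosis is present in 8/20 before and 14/20 after. Let a = present at both scans, b = gained, c = lost.

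- Fisher on 14/20 vs 8/20: p = 0.111, whatever the pairing.
- Unpaired log-RR SE = √(1/14 − 1/20 + 1/8 − 1/20) = 0.311, so RR = 14/8 = 1.75 (95% CI 0.95 to 3.22).
- Exact McNemar p = twice the smaller binomial tail of b against c with probability 0.5; for 6 and 0 it is 2 × 0.5⁶ = 0.031.
- Paired log-RR SE = √((b + c)/(14 × 8)); for b + c = 6 it is √(6/112) = 0.231.

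| a | b gained | c lost | McNemar p | Paired RR (95% CI) |
|---|---|---|---|---|
| 8 | 6 | 0 | 0.031 | 1.75 (1.11 to 2.75) |
| 7 | 7 | 1 | 0.070 | 1.75 (1.04 to 2.95) |
| 5 | 9 | 3 | 0.146 | 1.75 (0.92 to 3.32) |
| 4 | 10 | 4 | 0.180 | 1.75 (0.88 to 3.50) |

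Fisher gives one answer for all four rows. The paired variance is below the unpaired one exactly when a exceeds 14 × 8/20 = 5.6, the count expected if the scans were unrelated. The first two rows have positive within-patient association and narrower paired intervals. The last two have negative association and wider ones. The RR estimate itself does not change.

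**Step 2: rejection rates.** Each pair is a bivariate normal with latent correlation ρ, cut at the assumed prevalences. For 30% to 60% and ρ = 0.5, the cell probabilities are 0.2465 (both), 0.3535 (gained), 0.0535 (lost) and 0.3465 (neither). Summing over all multinomial tables with n = 20 gives:

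| Before → after | ρ | Fisher | Exact McNemar |
|---|---|---|---|
| 30% → 60% (power) | 0 | 35% | 34% |
| 30% → 60% (power) | 0.5 | 32% | 45% |
| 30% → 60% (power) | 0.7 | 30% | 51% |
| 30% → 60% (power) | 0.9 | 29% | 57% |
| 80% → 90% (power) | 0.5 | 4.5% | 3.1% |
| 40% → 40% (type I error) | 0.5 | 0.6% | 1.5% |
| 40% → 40% (type I error) | 0.7 | 0.2% | 0.8% |
| 40% → 40% (type I error) | 0.9 | 0.01% | 0.13% |

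Both tests lie far below 5% under no change, so part of the conservatism comes from exact testing with 20 pairs and not from the lost pairing. If the binary correlation were negative (−0.3, 40% at both scans), Fisher's type I error would be 4.7% and McNemar's 2.5%.

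**The case against.** A reader might infer that the plan prescribes Fisher's test for the before/after data, so that its p-values and intervals will be wrong. The documents do not support that. Section 7.1 leaves the contrast open, and the study has comparisons where Fisher and an RR fit: AF outcome by fibrosis status (a secondary objective) and patients against database controls, provided the age-sex matching is not individual. This part of the objection stands. The defect is an unassigned test and a missing paired one. Either way, the before/after categorical comparison has no suitable method named.

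The stated hypothesis also concerns fibrosis surface area, which is continuous, and no cut-off for presence or for an affected segment is given in sections 5.1.1 or 5.2. That stands as a limit on importance, although presence and location are named in the primary objective.

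It is also fair that the six-gained, none-lost table is the most favourable split for its margins, and that the power advantage vanishes at high baseline prevalence. Finally, this is a pilot without a power calculation, the loss is conservative under positive correlation, and a correct analysis can be run later on the same data. These points lower the urgency. They do not remove the gap, because section 7.1 commits to significance testing and 95% intervals.

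Reporting a Fisher p-value beside a separately computed RR interval is common practice and is not counted against the plan here.

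**Conclusion.** The concern holds as an omission: section 7.1 names one categorical method, for independent groups, without assigning it, and none for paired data. If Fisher were used before versus after, the expected harm is lost power and precision. It is not inflated false positives, and the RR estimate is not biased by it. Under an assumed rise from 30% to 60% and latent correlation 0.5 to 0.9, the loss is about 13 to 28 percentage points of power (45 − 32 and 57 − 29). It is nil at zero correlation and slightly reversed at 80% to 90%. The direction rests on positive within-patient correlation, which is plausible but not documented. The plan should be corrected before analysis, but the gap does not undermine the study or its data.

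**What to change.** In section 7.1:

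- **Presence before/after:** use the exact McNemar test, with a paired risk difference or paired RR and a 95% CI from the paired variance.
- **Location:** report paired changes per segment with CIs, labelled exploratory or adjusted for multiplicity. Do not pool segments across patients as independent observations. A paired comparison of the number of affected segments per patient may be added, but it measures extent and cannot detect relocation when the count is unchanged.
- **Fisher and RR:** restrict them to named independent-group contrasts, for example AF by fibrosis status, or patients against controls if matching is not individual. State which kind of matching is used.
- **Definitions:** state the threshold that makes fibrosis present and a segment affected.

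The cost is a few sentences and no new data or visits. SPSS, the package already named, offers McNemar's test, and the paired RR interval is the one-line formula shown above. The real work is agreeing the threshold before the scans are read. The trade-off is slightly lower power for McNemar when correlation is near zero or baseline prevalence is very high.
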